4.1 Discussion of Study Design

Refer to Section 1: Introduction for a description of the core IND 9836 study designs.

4.2 Study Treatment

The study treatment is thymus transplantation using allogeneic cultured postnatal tissue from unrelated donors under the age of 9 months (RVT-802). The tissue is sectioned upon harvest. Tissue slices are held in a tissue culture incubator with daily feeding for 12 to 21 days. After 2 to 3 weeks, the slices are brought to the operating room and inserted into the recipient's quadriceps muscles. Usually both quadriceps are used.

As specified in the individual study protocols, the dose planned for transplantation was the number of grams of transplanted tissue divided by the weight of the infant in kilograms or per square meter of BSA of the infant. In 2015, the IND was updated to define a dose range using the surface area of thymus tissue transplanted per recipient body surface area (IND 009836 Amendment Serial Number 209). Based on the 2015 IND amendment, to ensure consistency across study protocols, dosing will be reported in mm^2/m^2 for all studies.

Over the course of the clinical development program, there have been two thymus tissue manufacturing sites: [name] (DML) and the Good Manufacturing Process (GMP) Manufacturing Facility. Subjects transplanted under Protocols 668-1, 668-2, 884,

CONFIDENTIAL

Sponsor:	Enzyvant Therapeutics GmbH	Program:	RVT-802
----------	----------------------------	----------	---------

884.1, 931, 932, 950, 950.1, 735, and 33170 received RVT-802 manufactured by DML. Subjects transplanted under Protocols 25966 or 51692 could have received RVT-802 manufactured by either DML or GMP depending on the timing of transplantation.

For RVT-802 manufactured by DML, 4-6 thymus tissue slices were cultured on each plate. For each slice the millimeter dimensions were provided. The length (mm) by width (mm) surface area was calculated for each slice. If all of the thymus slices on a plate were not transplanted, e.g., 3 of 4 slices were used, then the dose received from that plate would be 75% of the plate dose. If it was unknown how many slices on a plate were transplanted, 50% of the plate dose was used. The total dose transplanted (mm^2/m^2) was the sum of the thymus tissue surface area (mm^2) divided by the recipient BSA (m^2) for each thymus slice transplanted.

For RVT-802 manufactured by GMP, the millimeter dimensions for each slice were not provided; only the number of slices transplanted and the total dose transplanted (mm^2/m^2) was supplied.

4.3 Study Schedule

Visit schedules vary among the seven core IND 9836 studies. Refer to the individual protocols for schematics of visit schedule.

4.4 Concomitant Medication

Immunosuppressive therapies and calcium/calcitriol (parathyroid recipients ONLY – Study 931) required per protocol will be summarized. Refer to the study protocols for specific details regarding protocol prescribed immunosuppressive therapy.

4.5 Study Analysis Populations

There are three analysis populations defined for these studies: the efficacy analysis set (EAS), modified efficacy analysis set (EAS-cDGA), and the full analysis set (FAS). Definitions for these populations are provided below.

CONFIDENTIAL

4.5.1 Efficacy analysis set (EAS)

The efficacy analysis set includes all subjects with athymia associated with complete DiGeorge anomaly or FoxN1 deficiency, who had no prior hematopoietic cell transplant (HCT) and were treated with RVT-802 allogeneic, cultured postnatal thymus tissue administered once by transplantation. Across the seven IND 9836 protocols, a total of 85 subjects are included in the EAS.

4.5.2 Modified efficacy analysis set (EAS-cDGA)

The modified efficacy analysis set includes all subjects in the EAS but excludes subjects without complete DiGeorge anomaly. Across the seven IND 9836 protocols, a total of 83 subjects are included in the EAS-cDGA.

4.5.3 Full analysis set (FAS)

The full analysis set is comprised of all patients receiving a thymus transplant in one of the IND 9836 protocols. Specifically, this is all subjects in the EAS plus infants with primary immunodeficiency associated with severe combined immunodeficiency (SCID) [n= 2], infants with cDGA that had received prior HCT [n= 4], and one patient that had received a prior fetal thymus transplant. Across the seven core IND 9836 protocols and three additional IND 9836 protocols (two single patient protocols and one expanded access protocol) a total of 93 subjects are included in the FAS.

4.6 Withdrawn Subjects

Handling of prematurely withdrawn subjects was not pre-specified in any of the protocols covered in this SAP.

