5.1.3.2.6. Prior attempts at immune reconstitution, such as bone marrow transplant

or previous thymus transplantation.

5.1.3.2.7. CMV Infection.

5.1.3.2.7.1. For Group 2, 3, and 4, CMV infection is documented by >500 copies/ml in blood by PCR on two consecutive assays.

5.1.3.2.8. Ventilator Dependence or Positive Pressure Support.

5.1.3.2.8.1. Ventilator support or positive pressure support, such as Continuous Positive Airway Pressure (CPAP) or Bi-level Positive Airway Pressure (BiPAP) support for a condition that is deemed to be severe or irreversible or which renders the subject too clinically unstable to undergo the procedures.

5.2. Withdrawal/Replacement of Subjects from Trial.

5.2.1. Removal of Subjects.

5.2.1.1. A subject may withdraw or be withdrawn from the study for any of the following reasons:

- if the parent(s) will not comply with the protocol, or
- if there are medical reasons not to proceed, or
- at the sponsor's discretion, or
- withdrawal of consent for any reason.

5.2.1.1.1. In all cases of study withdrawal, permission would be requested to receive updates on the subject's condition. This information would allow the Principal Investigator to better counsel parent(s) in the future.

5.2.1.1.2. With respect to the data analysis, any subject withdrawn because of lack of function of the thymus will be included in the data analysis. Their final data point at the time of withdrawal or at one year (if the parent(s) give permission for this sample and if no other treatment has been given) will be used in the calculations.

5.2.2. Replacement of Subjects.

5.2.2.1. There is no requirement for replacement of subjects.

6. Treatment of Subjects. Note that at the time of this amendment (November 2021) the clinical study is closed to enrollment. Patients currently remaining in the trial are all in the Post-Transplantation Period and have been returned to Care of Referring/Local Physician.

6.1. Assessment Periods-Thymus Graft Recipient.

6.1.1. Pre Transplantation Period.

6.1.1.1. This phase usually lasts from 2 to 8 weeks. The recipient is enrolled and screened. The recipient screening can be done as an inpatient or an outpatient.

6.1.2. Day of Operative Procedure(s).

6.1.2.1. Immediately after thymus transplantation, the subject will be an inpatient until medically stable.

- 6.1.3. Post Transplantation Period (From thymus transplantation to 24 months post-thymus transplantation).
 - 6.1.3.1. Duke University Medical Center (DUMC).

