6.2.1.8.2.1.3.1. A CBC with differential will be done weekly until the calcineurin inhibitor is weaned off. Once the calcineurin inhibitor is weaned off, the CBC will be done monthly as above.

6.2.1.8.2.2. Flow cytometry.

6.2.1.8.2.2.1. Flow cytometry, along with a CBC with (manual differential) (MD), is done to assess T, B, and NK cell numbers. Evaluation of naïve T cells is included.

6.2.1.8.2.2.2. Flow cytometry will be done as follows

- Month 3 ± 1 month
- Month 6 ± 1 month
- Month 9 ± 2 months
- Month 12 ± 2 months
- As medically indicated

6.2.1.8.2.2.3. Flow cytometry is done if there is an adverse event thought to be related to an increase in T or B cells. In particular, if the ALC remains greater than 4,000/mm³, and the subject has symptoms suggestive of autoreactive clones, the flow cytometry may be repeated sooner to help guide immunosuppressive therapy.

6.2.1.8.2.3. *In vitro* T cell proliferative responses to PHA.

6.2.1.8.2.3.1. PHA is done at Month 12 ± 2 months.

6.2.1.8.2.3.2. Additional testing may be done at the PI's discretion. If additional PHA testing is done, it is done in a CLIA or CAP Certified Laboratory.

6.2.1.8.2.4. TREC (T cell receptor rearrangement excision circles)

6.2.1.8.2.4.1. TREC data, if done, may be recorded.

6.2.1.8.2.5. Serum immunoglobulins including IgG, IgA IgM, and IgE.

6.2.1.8.2.5.1. Immunoglobulins are checked for evidence of development of IgA, IgM, and IgE.

6.2.1.8.2.5.2. Immunoglobulins levels are tested as follows

- Month 1 and 2
- Month 3 and 6 ± 1 month
- Month 9 and 12 ± 2 months

6.2.1.8.3. Testing for immune-based adverse events.

6.2.1.8.3.1. Complete Blood Counts with Differential.

6.2.1.8.3.1.1. Individuals with DiGeorge anomaly can have autoimmune

cytopenias.

6.2.1.8.3.1.2. The hemoglobin, platelet count and neutrophil counts are most important for surveillance for immune based adverse events.

6.2.1.8.3.2. Flow Cytometry.

6.2.1.8.3.2.1. The CD19 and/or CD20 antibodies will identify clonal or polyclonal amplifications of B cells. Such amplifications may be related to EBV and CMV infection.

6.2.1.8.3.3. Extended T cell receptor beta variable chain (TCRBV) flow cytometry.

6.2.1.8.3.3.1. This assay may be done to assess diversity of T cell receptor expression and to assess if new clones are developing, or is a single clonal population of T cells is developing.

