7.1. Specification of the efficacy parameters

7.1.1. Refer to 4.1

7.2. Methods and timing for assessing, recording, and analyzing of efficacy parameters.

7.2.1. The studies will be obtained on the time frame as detailed above. The data are recorded by the PI or the study staff as they accrue.

7.2.1.1. Efficacy data will be analyzed as outlined in the statistical analysis plan (SAP). See Appendix B.

8. Evaluation of Safety.

8.1. Specification of safety parameters.

8.1.1. Procedures to enhance research subject safety.

8.1.1.1. *Inpatient* subjects are monitored daily by physicians and staff familiar with management of immunodeficient patients. Subjects who are medically stable may be followed as *outpatients* at DUMC pre and post thymus transplantation.

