5.3.1 Efficacy Analysis Visit Windows

The efficacy endpoints in Section 2.2 were generally specified at year 1. In summary tables, both the year 1 and year 2 time points will be summarized, as applicable, and all data collected will be listed. Non-survival related efficacy data will be assigned visits using the rules assigned in the table below. In the case that there are multiple visits within the analysis window, then the visit closest to the target date will be used for analysis; if two visits are equidistant from the target date, then the later visit will be used.

In efficacy tables, if a subject has not yet reached the Year 1 or Year 2 visit, then that subject will not be included in the table summaries.

CONFIDENTIAL

Table 5.3.1.1 Efficacy Analysis Windows

Visit Name	Target Day	Window
Visit Name	Post-Transplant	Window
Month 6	182	[137, 227]
Year 1	365	[305, 425]
Year 2	731	[671, 791]

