5.10 Missing Values – Missing Visits

No imputation of missing data will be done.

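### SAP 4.6 denies a withdrawal rule that the current Study 25966 protocol contains, so a graft failure withdrawn before day 305 with no one-year sample drops out of the Year 1 naïve-CD4 summary

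*SAP*

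**What the plan says.** SAP 4.6 disposes of withdrawals in one sentence: "Handling of prematurely withdrawn subjects was not pre-specified in any of the protocols covered in this SAP". Study 25966 is one of the covered protocols (SAP Table 2.1 and section 5.2).

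Protocol 5.2.1.1.2 says that "any subject withdrawn because of lack of function of the thymus will be included in the data analysis". It then names the value: "Their final data point at the time of withdrawal or at one year (if the parent(s) give permission for this sample" and provided no other treatment has been given. The rule covers this one reason for withdrawal and no other.

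The protocol hands the efficacy analysis to the SAP. Section 7.2.1.1 reads: "Efficacy data will be analyzed as outlined in the statistical analysis plan (SAP). See Appendix B". Appendix B identifies that document as version 2 of 19 September 2018.

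Two SAP rules then decide which values reach the Year 1 tables. Section 5.3.1: "Non-survival related efficacy data will be assigned visits using the rules assigned in the table below". That table gives Month 6 as days 137 to 227 and Year 1 as days 305 to 425. Section 5.10: "No imputation of missing data will be done".

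**The concern.** Two documents in force together disagree. The protocol has a rule for withdrawal because the graft did not work. The SAP says no such rule exists, and its general rules lead to a different result.

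The difference is selective. The subjects concerned left because the thymus tissue was not functioning, so their naïve-CD4 counts would be expected to be low. Leaving them out of Year 1 can only be expected to raise the summary, in favour of the product. In a small uncontrolled study, a few omitted failures could visibly change the immune-reconstitution result.

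**Working it through.** **1. Check the windows.** For Year 1 the target is day 365, and 365 − 60 = 305 and 365 + 60 = 425, which matches SAP Table 5.3.1.1 and is close to the protocol's 12 ± 2 months. For Month 6, 182 − 45 = 137 and 182 + 45 = 227, which also matches. Days 228 to 304 (304 − 228 + 1 = 77 days) belong to no efficacy window.

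**2. Follow a last value through the SAP.** Take a subject withdrawn for lack of thymus function who has no one-year sample.

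| Day of last value | SAP efficacy window | In Year 1 under the SAP? | In the analysis under protocol 5.2.1.1.2? |
|---|---|---|---|
| before 137 (e.g. 100) | none | no, listing only | yes |
| 137–227 (e.g. 182) | Month 6 | no, Month 6 only | yes |
| 228–304 (e.g. 260) | none | no, listing only | yes |
| 305–425 | Year 1 | yes | yes |

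The documents therefore part only for a last value before day 305 with no one-year sample. A one-year sample taken inside the window enters Year 1 under either document. The windows and the no-imputation rule are enough to produce this result; no other SAP clause is needed.

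**3. Illustrate the size.** The documents do not say how many such subjects there were, so this is an example and not an estimate.

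- Evaluable subjects N: SAP Table 2.1 lists 24 transplanted in Study 25966. Protocol 9.2.1 anticipates about 25% early deaths. 24 × 0.75 = 18. This assumes that every survivor has a usable value.
- Omitted failures: one, with a value near 0 (assumption).
- If S is the sum of all N values and the omitted value is 0, the mean is S/N under the protocol rule and S/(N − 1) under the SAP. The ratio is N/(N − 1) = 18/17 = 1.059.

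The SAP mean would be about 6% too high. With no such subject the error is zero. A value above 0 gives a smaller error.

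**The case against.** **The protocol clause is loosely worded.** It speaks of inclusion in the data analysis and names no endpoint, visit or table. Such a subject still counts in the analysis sets, the survival analysis, disposition and the listings. This stands in part: applying the clause to Year 1 naïve CD4 is an inference. It is a reasonable one, because the clause names a final data point and offers a one-year sample as the alternative, and naïve CD4 at 12 months is a stated endpoint.

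**The SAP may have been right when written.** It dates from 2018 and the protocol from 2022. The change lists for the 2021 and 2022 amendments do not mention 5.2.1.1.2, which suggests that it is older than both, but nothing shows that it existed in 2018. A reader might infer that the SAP overlooked a rule already in place; the documents do not establish that. The present mismatch remains, because the current protocol still names this SAP.

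**Two stronger readings fail.** A reader might rely on the SAP 5.3.1 sentence "if a subject has not yet reached the Year 1 or Year 2 visit, then that subject will not be included" as excluding withdrawn subjects. Because it speaks of those who have not yet reached the visit, and an interim cut of ongoing studies was planned, it most naturally means subjects still in follow-up. A reader might also infer that any Month 9 flow value ends up only in listings. The protocol schedules that sample at "Month 9 ± 2 months". Around day 273, with two months taken as 60 days, that is days 213 to 333, so early values fall in Month 6 and late ones in Year 1. Only days 228 to 304 are unassigned.

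**Some information is already reported.** SAP 5.4 summarises reasons for discontinuation within two years, and all data are listed. That helps a reader find these subjects but does not put their values into Year 1. The label's pooled 12-month range (1 to 751) shows that low values are kept when they fall in the window; it says nothing about those outside it.

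**Conclusion.** The point holds in a limited form. SAP 4.6 is inaccurate against the current Study 25966 protocol for one class of withdrawal. Followed as written, the SAP omits from Year 1 any such subject whose last value precedes day 305 and who has no one-year sample. The expected direction of bias in the descriptive Year 1 immune summaries is upward.

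The size is unknown and may be nil. The 6% figure rests on an assumed single omission, a value near 0 and N = 18. It should not be read as evidence that reported results are biased.

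The primary survival analysis is unaffected. Nor does the absence of a formal test of the protocol 3.2.1 hypothesis on naïve CD4 above 100 add to this point: SAP 3.3 openly limits testing and refers additional hypotheses to project level.

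**What to change.** 1. Correct SAP 4.6 to cite protocol 5.2.1.1.2 for Study 25966 and to say that the rule covers withdrawal for lack of thymus function only.
2. State in SAP 5.3.1 and 5.10, as an exception for Study 25966, that such a subject enters the Year 1 naïve-CD4 summary with the one-year sample where it is available under the protocol's conditions, and otherwise with the final value at withdrawal. The protocol gives no order between the two values, so the SAP should set one.
3. Report the number of such subjects, even if zero, and show the Year 1 summary with and without them.

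The cost is a short SAP amendment and one extra display, with no new data. The drawback is that early values enter a Year 1 summary and the result may look slightly less favourable. The label's pooled naïve-CD4 median is 42 at 6 months against 212 at 12 months, so an early value may understate what a later sample would have shown. The paired display makes that visible.

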4.7 Randomisation

Not applicable. All studies were open label, uncontrolled, non-randomized studies.

4.8 Blinding

None of the protocols covered in this SAP were blinded: all subjects received the investigational medicinal product. Accordingly, the Investigator, study site personnel, representatives of the Sponsor and CRO were unblinded to study treatment.

4.9 Sample Size

Refer to Appendix 1 for individual study sample sizes.

CONFIDENTIAL

Sponsor:	Enzyvant Therapeutics GmbH	Program:	RVT-802
----------	----------------------------	----------	---------

5 Statistical Methodology

5.1 Planned Analyses

There are three analysis populations defined for these studies: the efficacy analysis set (EAS), modified efficacy analysis set (EAS-cDGA), and the full analysis set (FAS), which are defined in Section 3.5. Efficacy analyses will be carried out using the EAS and EAS-cDGA. The demographic and safety analysis will be carried out on the FAS.

Summary statistics will be presented for continuous variables, by way of n, mean, standard deviation (SD), median, quartiles, and ranges and by way of frequencies and percentages for categorical variables.

Survival will be evaluated one year and two years post-transplant.

All statistical analyses will be performed in SAS version 9.4 or later running on a validated platform.

5.2 Interim Analysis

Two protocols covered in this SAP are ongoing: protocols 25966 and 51692. An interim analysis of available data from subjects transplanted as of 15-JUL-2017 will be performed. As all studies are unblinded, this interim analysis poses no risk to the integrity of the ongoing protocol.

5.3 Visit Windows

Only data through two years post-transplant will be collected in the database, except survival, adverse events, and immunizations which were collected longer than two years. All CSR summaries will only go out until the two-year time point; the integrated summary of efficacy will explore long term survival (more than two years).

5.3.1 Efficacy Analysis Visit Windows

The efficacy endpoints in Section 2.2 were generally specified at year 1. In summary tables, both the year 1 and year 2 time points will be summarized, as applicable, and all data collected will be listed. Non-survival related efficacy data will be assigned visits using the rules assigned in the table below. In the case that there are multiple visits within the analysis window, then the visit closest to the target date will be used for analysis; if two visits are equidistant from the target date, then the later visit will be used.

In efficacy tables, if a subject has not yet reached the Year 1 or Year 2 visit, then that subject will not be included in the table summaries.

CONFIDENTIAL

Table 5.3.1.1 Efficacy Analysis Windows

Visit Name	Target Day	Window
Visit Name	Post-Transplant	Window
Month 6	182	[137, 227]
Year 1	365	[305, 425]
Year 2	731	[671, 791]

5.3.2 Safety Analysis Visit Windows

The safety endpoints in Section 2.4 were generally collected while at the hospital following transplantation. Further safety assessments were scheduled at months 3, 6, 9, 12, 18, and 24. Table summaries will only include the time points in the table below, and all data collected in the database will be listed. Data will be assigned visits using the rules assigned in the table below, where Day 0 is the day of transplant. In the case that there are multiple visits within the analysis window, then the visit closest to the target date will be used for analysis; if two visits are equidistant from the target date, then the later visit will be used.

Table 5.3.2.1 Safety Analysis Windows

Visit Name	Target Day	Window
Visit Name	Post-Transplant	Window
Pre-Transplant	n/a	[- ∞, -1]
Week 1	7	[1, 10]
Week 2	14	[11, 17]
Week 3	21	[18, 24]
Week 4	28	[25, 31]
Week 8	56	[49, 63]
Month 3	90	[65, 120]
Month 6	182	[152, 212]
Month 9	273	[243, 303]
Month 12	365	[335, 395]

CONFIDENTIAL

Month 18	548	[488, 608]
Month 24	731	[671, 791]

5.4 Disposition of Subjects

The number of subjects receiving study treatment, in each analysis population, status (ongoing, died, withdrew) and the reasons for any premature discontinuation from the study (most commonly death) will be summarized and listed. Premature discontinuation from the study was defined as study discontinuation within two years after transplantation.

5.5 Baseline and Demographic Characteristics

All baseline and demographic characteristics will be summarised for each protocol. This will include age on day of transplantation (in days), sex, race, ethnicity, height, weight, BSA, and relevant medical history. Baseline is defined as the last value obtained prior to thymus transplantation. For subjects who received RATGAM prior to the transplantation, baseline for flow cytometry, proliferation, and PHA values will be defined as the last value obtained prior to the initiation of the first dose of RATGAM. If multiple values are recorded on the same day, the average of all measurements taken on that day will be used as the baseline value.

Notes:

- BSA will be calculated using Haycock's formula:
 - $BSA (m^2) = 0.024265 \times (weight[kg])^{0.5378} \times (height[cm])^{0.3964}$
- Medical history will be coded according to MedDRA version 19.1.
- Relevant medical histories are all medical histories recorded in the CRF.
- Any duration [days] = end day – onset day + 1

